5. DISINFECTION PROCEDURES FOR MEDICAL EQUIPMENT USED ON BOTH HUMANS AND ANIMALS

N/A

6. PARTICIPANT POPULATION

a. Planned Enrollment

Accepting type I error of 0.05 with 90% power, we will require 107 participants per group to detect one unit between-group difference in NRS pain scale. We are proposing a more conservative (larger) sample size to: (1) preserve power if the effect size is underestimated secondary to low medication adherence; and (2) preserve power for our subgroup analyses. We will therefore add 50% to our sample size to a total of 160 patients in each arm. Correlation between repeated measure will decrease variance and increase the power of the proposed study.

b. Age, Gender, and Ethnic Background

Men and women of any ethnic background who are 18 years old or above will be enrolled.

c. Vulnerable Populations

We will not enroll potentially vulnerable subjects.

d. Rationale for Exclusion of Certain Populations

We are studying the comparative effectiveness of these two medications in adults. Study of chronic pain in children is beyond the scope of our study.

e. Stanford Populations

Not applicable

f. Healthy Volunteers

Not applicable

g. Recruitment Details

All adult patients with chronic pain receiving care from Stanford Pain Management Center will be assessed for eligibility by their treating pain physician during each clinical visit. If eligible, the treating pain physician will go through the oral consent script. If the patient consents to participate, he/she will be randomized to receiving either duloxetine or desipramine. Open label prescription will be then sent to participants' pharmacy.

h. Eligibility Criteria

i. Inclusion Criteria

1. Age of 18 years old or above
2. Persistent pain for more than 3 months
3. Candidate for treatment by anti-depressant based on treating pain provider

ii. Exclusion Criteria

1. Prior failure of duloxetine and/or desipramine (patients who have failed other TCAs or SNRIs can be considered for the trial based on the reason for previous medication failure)
2. Contraindication to taking duloxetine or desipramine
3. Patient refusal

i. **Screening Procedures**

We do not collect any PHI prior to enrollment.

j. **Participation in Multiple Protocols**

Participants will be asked if they are enrolled in any other research study.

k. **Payments to Participants**

Participants will not receive any payment for taking part in this study.

l. **Costs to Participants**

Cost of the study medication will be borne by the participants and/or insurance company as part of standard of care. The study itself does not incur any cost in addition to standard of care.

m. **Planned Duration of the Study**

We estimate the study to be completed in 5 years as below:

1. Enrollment: 48 months
2. Follow up for last enrolled patient: 6 months
3. Data analysis and reporting the results: 6 months

7. **RISKS**

a. **Potential Risks**

i. **Investigational devices**

None

ii. **Investigational drugs**

None

iii. **Commercially available drugs, biologics, reagents or chemicals**

Potential adverse events are based on package insert approved by United States Food and Drug Administration:

Duloxetine

Reactions are categorized by body system according to the following definitions: frequent adverse reactions are those occurring in at least 1/100 patients; infrequent

adverse reactions are those occurring in 1/100 to 1/1000 patients; rare reactions are those occurring in fewer than 1/1000 patients.

Cardiac Disorders — Frequent: palpitations; Infrequent: myocardial infarction and tachycardia.

Ear and Labyrinth Disorders — Frequent: vertigo; Infrequent: ear pain and tinnitus.

Endocrine Disorders — Infrequent: hypothyroidism.

Eye Disorders — Frequent: vision blurred; Infrequent: diplopia and visual disturbance.

Gastrointestinal Disorders — Frequent: flatulence; Infrequent: eructation, gastritis, halitosis, and stomatitis; Rare: gastric ulcer, hematochezia, and melena.

General Disorders and Administration Site Conditions — Frequent: chills/rigors; Infrequent: feeling abnormal, feeling hot and/or cold, malaise, and thirst; Rare: gait disturbance.

Infections and Infestations — Infrequent: gastroenteritis and laryngitis.

Investigations — Frequent: weight increased; Infrequent: blood cholesterol increased.

Metabolism and Nutrition Disorders — Infrequent: dehydration and hyperlipidemia; Rare: dyslipidemia.

Musculoskeletal and Connective Tissue Disorders — Frequent: musculoskeletal pain; Infrequent: muscle tightness and muscle twitching.

Nervous System Disorders — Frequent: dysgeusia, lethargy, and paresthesia/hypoesthesia; Infrequent: disturbance in attention, dyskinesia, myoclonus, and poor quality sleep; Rare: dysarthria.

Psychiatric Disorders — Frequent: abnormal dreams and sleep disorder; Infrequent: apathy, bruxism, disorientation/confusional state, irritability, mood swings, and suicide attempt; Rare: completed suicide.

Allergic: Skin rash, petechiae, urticaria, itching, photosensitization (avoid excessive exposure to sunlight), edema (of face and tongue or general), drug fever, cross-sensitivity with other tricyclic drugs Hematologic: Bone marrow depressions including agranulocytosis, eosinophilia, purpura, thrombocytopenia

Gastrointestinal: Anorexia, nausea and vomiting, epigastric distress, peculiar taste, abdominal cramps, diarrhea, stomatitis, black tongue, hepatitis, jaundice (simulating obstructive), altered liver function, elevated liver function tests, increased pancreatic enzymes

Endocrine: Gynecomastia in the male, breast enlargement and galactorrhea in the female; increased or decreased libido, impotence, painful ejaculation, testicular swelling; elevation or depression of blood sugar levels; syndrome of inappropriate antidiuretic hormone secretion (SIADH)

Other: Weight gain or loss; perspiration, flushing; urinary frequency, nocturia; parotid swelling; drowsiness, dizziness, proneness to falling, weakness and fatigue, headache; fever; alopecia; elevated alkaline phosphatase"

iv. Procedures

None

v. Radioisotopes/radiation-producing machines

None

vi. Physical well-being

Not applicable

vii. Psychological well-being

Not applicable

viii. Economic well-being

Not applicable

ix. Social well-being

Not applicable

x. Overall evaluation of risk

Low

b. International Research Risk Procedures

Not applicable

c. Procedures to Minimize Risk

Study medications will be administered as open label prescription. Both duloxetine and desipramine are commercially used medications at Stanford Pain Management Center; hence, all our clinicians have extensive experience in prescribing these medications and monitoring participants afterwards. We will continue safety monitoring procedure of Stanford Pain Management Center for these medications which includes regular follow-up visits as well as an open line of communication with nurses and physicians of our clinic. Moreover, the participants will have the contact information of the protocol directors and can consult them with any further questions or concerns.

d. Study Conclusion

The study will terminate at the completion of follow-up for last patient enrolled. Study medication will be stopped if the participant decides to discontinue the medication. Since the medications used are part of standard clinical care that the patients receive in our clinic, the participants can continue the medication after the completion of the study if they would like to.

e. Data Safety Monitoring Plan (DSMC)

i. Data and/or events subject to review

The treatments in the study are not different from routine clinical practice; therefore, adverse events will be monitored as a part of participants' clinical care by their clinic providers. Protocol Director (PD) will monitor for protocol deviations.

ii. Person(s) responsible for Data and Safety Monitoring

Data and safety will be monitored by investigators and PD.

iii. Frequency of DSMB meetings

N/A

iv. Specific triggers or stopping rules

N/A

v. Will the Protocol Director be the only monitoring entity? (Y/N)

Yes

f. Risks to Special Populations

N/A

8. BENEFITS

There is no potential benefit related to participation in the study.

Any benefit can be attributed to clinical administration of these two medications that are commonly used in adult patients with chronic pain.

9. PRIVACY AND CONFIDENTIALITY

All participant information and specimens are handled in compliance with the Health Insurance Portability and Accountability Act (HIPAA) and privacy policies of Stanford University, Stanford Health Care, and Stanford Children's Health.

Comparing Effectiveness of Duloxetine and Desipramine in Patients With Chronic Pain: A Pragmatic Trial Using Point of Care Randomization

Statistical Analysis Plan

NCT03548454

Revised March 28, 2025

Statistical Analysis. The initial sample size calculation determined that 107 participants per group would provide 90% power to detect a one-unit between-group difference in the NRS pain score ($SD=2.25$) at $\alpha=0.05$. However, the study was prematurely stopped due to most referred patients having prior experience with duloxetine or, less frequently, desipramine. As a result, we enrolled 38 patients in the desipramine group and 48 in the duloxetine group. With this sample size, we could detect a difference of 1.37–1.58 in NRS pain reduction with 80–90% power.

Participants were eligible if they completed at least one survey before being assigned a study medication and at least one follow-up survey. The baseline assessment was defined as the most recent survey before treatment assignment. Participants without follow-up surveys or those lost to follow-up were excluded. The primary analysis followed modified intention-to-treat (ITT) principles. However, within the first day of treatment assignment, five individuals switched from desipramine to duloxetine. To account for these switches, a per-protocol (PP) analysis was conducted, categorizing individuals based on the medication they took. For consistency, survey data (research and clinical surveys) were evaluated up to 52 weeks post-baseline when available.

Baseline demographic and clinical characteristics were summarized using three comparative analyses. First, a “per-protocol” approach was applied to compare demographic and clinical characteristics between the desipramine and duloxetine groups. Second, differences were assessed between participants who completed the full course of medication and those who discontinued early. Third, participants who achieved a clinically meaningful ($\geq 30\%$) pain reduction were compared to those who did not. Categorical variables were analyzed using Pearson’s Chi-square or Fisher’s Exact tests, while continuous variables were assessed using t-tests or Mann-Whitney U tests depending on normality.

Longitudinal changes in pain intensity, physical function, and psychological function were analyzed using linear mixed-effects models (LMMs). Dependent variables included pain intensity (average and worst), PROMIS Pain Interference, PROMIS Anxiety, PROMIS Depression, and PROMIS Physical Function (Upper Extremity, Mobility, and Composite) scores. The primary independent variables were medication group (desipramine vs. duloxetine) and its interaction with time (weeks since baseline) to assess differential treatment effects. Baseline pain intensity was included as a covariate. A random intercept for each participant accounted for within-subject correlations. Various model structures were evaluated using Akaike Information Criterion and Bayesian Information Criterion, with final models selected based on model fit and diagnostic assessments. Model fit was evaluated using residual plots, Q-Q plots, histograms, and Variance Inflation Factor analyses. Bonferroni correction was applied to account for multiple comparisons. LOESS (Locally Estimated Scatterplot Smoothing) predicted values with 95% confidence intervals were plotted to visualize longitudinal trends stratified by medication group.

Kaplan-Meier survival analysis was used to evaluate medication adherence over time, conducted separately for both the intention-to-treat and per-protocol analyses. Time to discontinuation was calculated as the number of days between treatment initiation and discontinuation. Participants who completed the full course of medication were censored at the maximum observed follow-up duration. Kaplan-Meier survival curves were generated for each medication group, and the log-rank test was used to compare groups with 95% confidence intervals. A Kaplan-Meier survival analysis was also conducted to compare the time to achieving a $\geq 30\%$ reduction in average pain intensity from baseline between medication groups. A binary indicator variable was created to determine whether a participant met the pain reduction threshold at any follow-up point, with time-to-event defined as the earliest occurrence of this reduction. Participants who did not achieve the threshold were censored at 52 weeks. Kaplan-Meier survival curves were plotted separately for desipramine and duloxetine, with the log-rank test used for group comparisons.

To assess the relationship between medication adherence and the likelihood of achieving meaningful pain reduction, a chi-square test was conducted. The proportion of participants who achieved a $\geq 30\%$ pain reduction was compared between those who completed the full course of medication and those who discontinued early

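### Mixed-model weeks and the 52-week window start at a pre-assignment survey with no age limit, so they include untreated time; the origin for time to response is not stated

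*SAP*

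**What the plan says.** All SAP references are to its single section, Statistical Analysis.

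- **Baseline.** "The baseline assessment was defined as the most recent survey before treatment assignment". No maximum age is given. The inclusion rule for the analysis sets no window either: "Participants were eligible if they completed at least one survey before being assigned a study medication and at least one follow-up survey".
- **Model time.** The mixed models use medication group and "its interaction with time (weeks since baseline) to assess differential treatment effects".
- **Data window.** "survey data (research and clinical surveys) were evaluated up to 52 weeks post-baseline when available".
- **Time to 30% pain reduction.** The event is defined, "with time-to-event defined as the earliest occurrence of this reduction", and so is censoring: "Participants who did not achieve the threshold were censored at 52 weeks". No start date is given.
- **Time to discontinuation.** "Time to discontinuation was calculated as the number of days between treatment initiation and discontinuation".

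In the protocol, section 2a (Data collection) describes monthly electronic surveys that already belong to routine care. Section 2a (Randomization) places randomisation at the clinic visit, done electronically through the registry. Neither requires a survey on the day of randomisation. Section 6g has the prescription sent to the participant's pharmacy after randomisation.

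**The concern.** By the SAP's own definitions, week 0 of the longitudinal models is the date of a survey completed before the patient had a study drug. The interval from that survey to assignment is untreated time, yet it counts as follow-up. If it varies, the same labelled week means different lengths of time since assignment in different patients.

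Three things are at stake:

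- the time axis of the model estimates and LOESS curves, where early change would be smeared;
- the amount of post-assignment follow-up inside the 52-week window, which would be cut at a different point for each patient;
- the reported time to response, if it uses the same clock.

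The SAP also uses at least two time origins without saying how they relate.

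**Working it through.** **The plan's own figures.** With SD 2.25, two-sided alpha 0.05 and 90% power for a 1-unit difference, n = 2 × (1.960 + 1.282)² × 2.25² / 1² = 106.4, so 107 per group, as stated. With 38 and 48 patients, the detectable difference is (1.960 + z_power) × 2.25 × √(1/38 + 1/48), which gives 1.37 at 80% and 1.58 at 90% power, also as stated. Neither figure depends on the time origin, so they do not bear on this point.

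**Which clock applies where.**

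| Analysis | Origin in the SAP |
|---|---|
| Mixed models | baseline survey (explicit) |
| 52-week data window | baseline survey (explicit) |
| Time to discontinuation | treatment initiation (explicit) |
| Time to 30% reduction | not stated |

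**Effect of a gap of L weeks on the window and labels.** Follow-up after assignment inside the window is at most 52 − L. An event 8 weeks after assignment is labelled week 8 + L on the baseline clock. L is not in the documents, so a range is shown.

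| L (weeks, assumed) | Weeks after assignment inside window | Label for an event at week 8 |
|---|---|---|
| 0 | 52 | 8 |
| 1 | 51 | 9 |
| 4 | 48 | 12 |
| 8 | 44 | 16 |
| 12 | 40 | 20 |

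**Median time to response, if counted from baseline.** This was simulated with 40,000 patients. SD 2.25 is from the SAP. Assumed: baseline NRS mean 6, intraclass correlation 0.6, a 1.7-point fall reached at 8 weeks, monthly surveys, and gaps uniform over the range shown. With survey dates spread over the month, the median from assignment is 8.8 weeks.

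| Assumed gap (weeks) | Median on baseline clock | Shift |
|---|---|---|
| 0–4 | 11.0 | 2.2 |
| 0–8 | 13.2 | 4.4 |
| 0–12 | 15.5 | 6.7 |

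If every patient is surveyed at exact months after assignment, the 0–4 week case moves from 8.7 to about 11.5 weeks. That shift of 2.8 is partly an artefact of the median sitting on a step in the survey grid, so the spread-out dates are the better guide.

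**Mixed model.** If the true group difference w weeks after assignment is D(w), the model on the baseline clock reports about D(w − L) at labelled week w. With a linear effect and a constant L, only the intercept moves and the slope does not. If D reaches 1.0 at week 26, the expected value at labelled week 26 is (26 − L)/26. For a mean gap of 2 weeks that is 24/26 = 0.92, and for a mean gap of 6 weeks 20/26 = 0.77.

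Simulation agrees. Assumptions: 38 and 48 patients, 4-weekly surveys, random intercept, baseline covariate, between- and within-patient SD 1.8 and 1.35.

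- Gaps 0–4 weeks: the difference at week 26 is 1.02 timed from assignment and 0.94 timed from baseline.
- Gaps 0–12 weeks: 1.00 and 0.76.
- In both cases the group-by-time slope is essentially unchanged.
- The slope was clearly diluted only with long, skewed gaps (exponential, mean 12 weeks): −0.026 per week on the baseline clock against −0.035 timed from assignment in the same runs, true value −0.038. That case had 40 runs and is rough.

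**The case against.** The strongest points on the other side are these.

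- **The response clock is not stated.** In the response definition, the reference to baseline fixes the value against which 30% is measured, not a start date. This stands. A reader might infer from the matching 52 weeks that response is timed from baseline, but the SAP does not say so, and the shift in the median is conditional on that reading.
- **The SAP does not call these weeks on treatment.** It labels them as weeks since baseline. This also stands, so the labels are not false. They are simply not the quantity a reader of a treatment trial will take them for.
- **The gap may be short.** With monthly routine surveys, a patient who answers each one would have a gap of about 0 to 4 weeks, or days if the survey was completed for the visit. Nothing in the documents suggests that 8 to 12 weeks is typical. Missed surveys could lengthen the gap, and nothing caps it.
- **The arms are treated alike.** The gap is fixed before randomisation, so its distribution should be the same in both arms on average. A reader might infer that the comparison of drugs is biased; the documents give no ground for that. With 38 and 48 patients a chance imbalance is possible, and reporting the gap by arm would show it.
- **Different endpoints may have different origins.** True. Assignment and initiation can also differ, since the prescription goes to a pharmacy. What is needed is that each origin is stated and suits its analysis population.

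None of this removes the explicit part: the mixed models and the data window start before assignment.

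**Conclusion.** The concern holds as a minor point about the time axis. On the SAP's wording, model time and the 52-week window include untreated time that varies between patients, while discontinuation is timed from initiation and response has no stated origin.

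The size depends on a gap the documents do not give. For assumed gaps of 0–4 weeks, the range best supported by monthly surveys, the group difference at labelled week 26 falls by about 8% (1.02 to 0.94) if the effect grows linearly. The median time to response would be about 2 weeks too long if it is counted from baseline. Older baseline surveys make both effects larger; same-day surveys make them negligible.

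It would go too far to say that the arm comparison is biased, that the group-by-time test is materially weakened, or that response times are certainly overstated.

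**What to change.** - Count weeks from treatment assignment (randomisation) in the mixed models, the LOESS plots and the time-to-response analysis, and set the 52-week window from the same date.
- Keep the last pre-assignment survey only as the baseline value: the covariate and the reference for the 30% reduction.
- State the origin for each survival analysis, using assignment for the intention-to-treat versions.
- Report the distribution of the survey-to-assignment gap by arm.
- Optionally, repeat the analyses with recent baseline surveys only. Any cutoff for recent is a choice the documents do not supply and should be given as such.

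The cost is one date subtraction per patient and a rerun. Randomisation was planned as an electronic step in the registry, so the assignment date should already be on record. No new data are needed.

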2. STUDY PROCEDURES

a. Procedures

Study Design: We will conduct a prospective open label randomized trial comparing effectiveness of duloxetine and desipramine.

Randomization (research): After obtaining research informed consent, the participants are going to be randomized by the treating pain provider using point of care randomization during the clinic visit. Point of care randomization will be done through Collaborative

Health Outcomes Information Registry (CHOIR) using computer generated random numbers.

Intervention: (standard of care) The participants are going to receive either duloxetine or desipramine. Duloxetine will be started at 20 mg per day. It will be increased to 40 mg per day at the beginning of week two, and then to 60 mg per day at the beginning of week three. Desipramine will be started at 25 mg per day. It will be increased to 50 mg per day at the beginning of week two, and then to 75 mg per day at the beginning of week three. These treatments will be continued for at least 6 months provided that the patients can tolerate the side effects and are willing to continue the treatment. Further titration of doses based on participants' tolerance and response is allowed based on clinical decision of the treating pain provider. Concomitant use of other analgesics or pain medications as well as pain interventions are also allowed.

Data collection: (standard of care and research) The participants are going to receive monthly electronic surveys which are already part of their routine clinical care. These surveys are going to be abbreviated to include average and worst Numerical Rating Scale (NRS) of pain; National Institute of Health (NIH) Patient Reported Outcomes Measurement Information System (PROMIS) measures for function, depression and pain interference; and questions about medication compliance, dose and adverse events. Data about use of other analgesics and medications, and pain interventions will also be recorded at these intervals from participants' electronic health records. If the participants do not complete the surveys within five days of receipt of the survey link, they will be contacted to be reminded of the survey. We will also record participants' baseline characteristics including age, sex, main pain diagnosis, other pain diagnoses, psychological comorbidities, medical comorbidities, medication use, and education.

b. Procedure Risks

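### The mixed models adjust only for pain at the single most recent pre-assignment survey; any earlier recent surveys, and each outcome's own baseline, are an unused and modest source of precision

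*SAP*

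**What the plan says.** The SAP's eligibility sentence requires that a patient "completed at least one survey before being assigned a study medication", plus at least one follow-up survey. It then fixes baseline: "The baseline assessment was defined as the most recent survey before treatment assignment". In the mixed-model paragraph, "Baseline pain intensity was included as a covariate", and "A random intercept for each participant accounted for within-subject correlations". The outcomes include average and worst pain and several PROMIS scores, but pain is the only baseline covariate named. The primary terms are medication group and its interaction with time. No averaging of earlier surveys is described, and no sensitivity analysis on the baseline definition.

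Protocol section 2a (Data collection) describes "monthly electronic surveys which are already part of their routine clinical care". After baseline, the SAP already uses clinical as well as research data: "survey data (research and clinical surveys) were evaluated up to 52 weeks post-baseline when available".

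**The concern.** A pain rating from one survey mixes a patient's usual level with short-term fluctuation, so it predicts later pain less well than an average of recent ratings usually does. Patients are recruited from those already in care at the centre, where monthly surveys are called routine. The SAP has to choose the latest survey, which suggests that some patients have more than one. Earlier scores precede assignment, so using them cannot bias the randomised comparison.

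What is at stake is precision. The trial enrolled 38 + 48 = 86 patients against 107 planned per group before inflation. Unadjusted power for the planned one-unit difference is about 53% at that size. Better use of data already held is one of the few remaining ways to improve precision. Separately, adjusting a PROMIS outcome for baseline pain alone leaves out its own baseline, which would normally be the better predictor.

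**Working it through.** **1. The plan's own figures.** Inputs from the SAP: SD 2.25, α 0.05 (two-sided reproduces the plan; one-sided would give 87 per group), 38 and 48 patients.
- Planned size: 2 × 2.25² × (1.960 + 1.282)² / 1² = 106.4, so 107 per group. Reproduced.
- SE = 2.25 × √(1/38 + 1/48) = 0.4886. Detectable difference: 2.802 × 0.4886 = 1.37 at 80% power and 3.242 × 0.4886 = 1.58 at 90%. Reproduced.

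Both use the raw SD. No baseline adjustment enters, so the baseline rule does not affect them.

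**2. Model for the gain.** The documents give no correlation between surveys, so a range is assumed. The variance of a pain score is split into a stable between-patient share *s*, a share *d* whose correlation decays as *a* to the power of the gap in months, and independent noise 1 − *s* − *d*. Let F be the follow-up quantity (mean of months 1–6, or month 6) and B the mean of the pre-assignment surveys, used only as a covariate. In units of 2.25²:

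variance factor = Var(F) − Cov(F,B)² / Var(B)

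80%-power detectable difference = 1.369 × √(variance factor)

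Example, *s*/*d*/noise = 50/20/30%, *a* = 0.8, second survey one month earlier, F = mean of months 1–6:
- One survey: 0.686 − 0.5984²/1 = 0.328; detectable difference 0.78.
- Two surveys: 0.686 − 0.5885²/0.83 = 0.269; detectable difference 0.71.
- Variance cut: 1 − 0.2687/0.3280 = 18%.

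**3. Range, if every patient has a second survey.**

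| s/d/noise (%), a | Gap (months) | Cut, mean of months 1–6 | Detectable difference, mean | Cut, month 6 |
|---|---|---|---|---|
| 70/0/30 | any | 33% | 0.70 → 0.57 | 17% |
| 50/20/30, 0.8 | 1 | 18% | 0.78 → 0.71 | 8% |
| 30/50/20, 0.9 | 2 | 7.4% | 0.775 → 0.746 | 3.3% |
| 30/50/20, 0.8 | 1 | 5.8% | 0.839 → 0.814 | 2.4% |
| 30/50/20, 0.8 | 2 | 3.4% | 0.839 → 0.824 | 2.4% |
| 30/50/20, 0.8 | 3 | 1.5% | 0.839 → 0.832 | 2.3% |
| 20/60/20, 0.8 | 3 | −1.9% (a loss) | 0.862 → 0.870 | 0.8% |

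The last row lies just outside the assumed range (*s* from 30 to 70%). It shows that with strong decay a simple mean can do slightly worse than the latest value.

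**4. If only some patients have a second survey.** With constant correlation 0.5 and six monthly follow-ups, the SE of the adjusted mean difference is 0.284 with one survey each, 0.263 if half have two, and 0.246 if all have two. In variance terms, 1 − (0.263/0.284)² = 14% and 1 − (0.246/0.284)² = 25%. The gain is therefore roughly proportional to the share of patients with a second survey. This calculation weights each patient's baseline by its reliability; an unweighted mean may gain a little less.

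**5. Group-by-time term.** In the same model, the SE of the 26-week interaction contrast is 0.4955 with one, two or three baseline surveys. With a random intercept and balanced visits it is estimated within patients, so a better baseline adds nothing.

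**The case against.** The strongest case against the point is that the last value before assignment is a conventional and unbiased baseline, and nothing in the plan is contradicted by using it. That stands: this is a missed efficiency option and not an error.

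Four stronger readings are tempting, and the documents do not support them.
- *Usable earlier surveys certainly exist and are being discarded.* The protocol's sentence on monthly surveys describes data collection for enrolled participants, even though it calls the surveys routine. The SAP guarantees one prior survey, and it speaks of referred patients, who may be new to the clinic. With one survey per patient the gain is zero.
- *All tests lose precision.* The group-by-time coefficient does not, under the conditions in step 5.
- *The 1.37–1.58 limit would improve.* It contains no baseline adjustment. Most of the distance from 1.37 to 0.71 in the example comes from ordinary adjustment and from averaging six follow-ups; the second survey contributes only 0.78 to 0.71.
- *The averaged baseline should replace the current one.* The SAP is dated March 2025 and reports final enrolment. Changing the main covariate now would be a post hoc switch.

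**Conclusion.** The point holds in a limited, conditional form. Where patients have a second recent survey before assignment, ignoring it makes the adjusted group difference somewhat less precise. If all had one, the variance cut would be about 1.5–33% for the months 1–6 mean and about 2–17% at month 6. The upper ends require no decay in correlation; the lower ends come from a large decaying share with monthly autocorrelation 0.8.

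These figures rest on assumed covariance structures, on 38 and 48 patients all being analysed, and on an unstated number of earlier surveys. Validity is not in question. The separate matter of adjusting PROMIS outcomes only for baseline pain does not depend on earlier surveys existing; its size was not computed, because the documents give no correlations between outcomes. Priority is low: a worthwhile refinement.

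**What to change.** 1. Adjust each outcome's mixed model for that outcome's own baseline score, not only for baseline pain.
2. Report how many patients in each group have two or more surveys in a fixed window before assignment, for example 90 days.
3. Add a clearly labelled supplementary analysis that uses the mean of the surveys in that window, or the earlier mean as a second covariate, with the single survey where only one exists. Keep the most-recent-survey baseline as the main definition.

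The cost is a few lines of SAP text and one derivation step on any earlier surveys already held; no new data collection is needed. The downside is that older scores are less current and baseline noise then differs between patients. With strongly decaying correlation, a simple mean may gain nothing or lose about 2% in variance. The fixed window limits this, and entering the earlier mean as a separate covariate lets the data set its weight.
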